Brain Imaging	Participants with a history of brain metastasis or symptoms should have surveillance MRIs (without and with contrast) per standard of care (approximately Q12W) or sooner if clinically indicated. CT of the brain without and with contrast can be performed if MRI is contraindicated. See Section 9.1.1.1 for further details.								
Clinical Outcomes Assessments									
NSCLC-SAQ	X					X		X	Completed electronically prior to dosing on Day 1 of each cycle from Cycle 1 and then every cycle thereafter for the remainder of the treatment period. See Section 9.1.2 for further details.
FACT-G7	X					X		X	
EQ-5D-5L	X					X		X	
PGIS	X					X		X	
PGIC						X		X	Completed electronically prior to dosing on Day 1 of each cycle from Cycle 2 and then every cycle thereafter for the remainder of the treatment period. The PGIC is not administered on C1D1. See Sections 9.1.2 and 9.1.2.4 for further details.

Table 2-2: On Treatment Procedural Outline (CA020016)

Procedure	Cycle 1 ^a Visit Window = -3 Days for C1D1, ± 3 Days for All Others					Each Subsequent Cycle		EOT	Notes ^b 1 Cycle = 6 Weeks
	D1	D8	D15	D22	D29	D1 (± 3 Days)	D22 (± 3 Days)		
Study Intervention									
IRT Randomization	X								Participant must receive the first dose of study medication within 3 calendar days from vial allocation.
BMS-986207 or Placebo	X			X		X	X		BMS-986207 600 mg Q3W. See Sections 5.1.2 and 7.1 for further details. Details of study drug preparation are found in the Pharmacy Manual.
Nivolumab	X			X		X	X		Nivolumab 360 mg Q3W. Participants may be dosed no less than 19 days from the previous dose.
Ipilimumab	X					X			Ipilimumab 1 mg/kg Q6W. Use body weight for dosing calculations. It is not necessary to re-calculate subsequent doses if the participant weight is within 10% of the baseline weight or the weight used to calculate the previous dose. Round all doses to the nearest milligram per institutional standard.

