Procedure	Safety Follow-up (relative to the last dose of study intervention) ^a			Imaging Follow-up (assessed Q12W for 2 years from last dose of study intervention) ^b	Survival Follow-up (assessed Q12W for 4 years from randomization) ^b	Notes ^c
	Follow-up 1 30 Days (± 7 Days)	Follow-up 2 60 Days (± 7 Days)	Follow-up 3 100 Days (± 7 Days)			
Tumor Assessments						
Body Imaging				X		For participants who have not experienced BICR-confirmed PD radiographic assessments, or who discontinue study intervention for reasons other than PD, contrast-enhanced CT of the chest and CT/MRI of the abdomen, pelvis, and all other known and/or suspected sites of disease should continue Q6W (± 7 days) starting from date of randomization until Week 48, and then Q12W (± 7 days) beginning on Week 49 until BICR confirmed disease progression, death, or withdrawal of consent, whichever occurs first. See Section 9.1.1.1 for further details.
Brain Imaging				X		Participants with a history of brain metastasis or symptoms should have a surveillance MRI (without and with contrast) per standard of care (approximately every 12 weeks), or sooner if clinically indicated. CT of the brain without and with contrast can be performed if MRI is contraindicated. See Section 9.1.1.1 for further details.

Table 2-3: Long-term Follow-up Procedural Outline (CA020016)

Procedure	Safety Follow-up (relative to the last dose of study intervention) ^a			Imaging Follow-up (assessed Q12W for 2 years from last dose of study intervention) ^b	Survival Follow-up (assessed Q12W for 4 years from randomization) ^b	Notes ^c
	Follow-up 1 30 Days (± 7 Days)	Follow-up 2 60 Days (± 7 Days)	Follow-up 3 100 Days (± 7 Days)			
PK and Immunogenicity Assessments	Refer to PK/Immunogenicity collection table in Section 9.5 for timing of collections.					
Biomarker Collection and Assessments	Refer to biomarker collection table in Section 9.8 for timing of collections.					
Clinical Outcome Assessments						
NSCLC-SAQ	X	X	X		X	To be completed electronically at Safety Follow-Up (Visits 1, 2, and 3 after last dose or date of treatment discontinuation) and only during Survival Follow-up beginning every 12 weeks from Follow-up Visit 3 (100 day Safety Follow-up). To be completed prior to any other study procedure. See Section 9.1.2 for further details.
FACT-G7	X	X	X		X	
EQ-5D-5L	X	X	X		X	

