
 To characterize the PK and immunogenicity of BMS-986207, nivolumab, and ipilimumab when administered in combination 	
 Summary measures of C_{trough} and EOI concentrations, incidence of ADA to BMS-986207, nivolumab, and ipilimumab, summary measures of ADA titers and kinetics (onset and duration), and assessments of ADA effect on efficacy, safety, and PK

 To explore the pharmacodynamic activity of BMS-986207 administered in combination with nivolumab and ipilimumab via assessment of translational biomarkers 	
 Summary measures of change (or % change) from baseline in intratumoral and peripheral biomarkers of immune activation and their association with anti-tumor activity

Table 4-1: Objectives and Endpoints

Objectives	Endpoints

 To explore potential associations between anti-tumor activity and select biomarker measures in the tumor and peripheral blood prior to treatment 	
 Summary measures of anti-tumor activity by pretreatment level of biomarkers of interest

 To characterize the threshold for meaningful change in disease-related symptoms as measured by the NSCLC-SAQ in participants with Stage IV NSCLC 	
 Analysis of meaningful change threshold for the NSCLC-SAQ total score based on the PGIS and PGIC as anchor measures

 To characterize changes in disease related symptoms and health-related quality of life in participants with Stage IV NSCLC 	
 Mean change from baseline in NSCLC-SAQ total score and FACT-G7

 To characterize patient-reported health status in participants with Stage IV NSCLC 	
 Mean change from baseline in EQ-5D-5L utility index and EQ VAS scores

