5.2 Number of Participants

Approximately 180 randomized participants are expected to be randomized in a 2:1 ratio to the 2 treatment arms stratified by PD-L1 expression and histology in pre-specified subgroups.

To ensure the randomized population is representative of the NSCLC population and to allow for appropriate subgroup analyses, total enrollment and/or enrollment in specific PD-L1 subgroups may be adjusted to ensure enrollment of at least 105 randomized participants with tumor cell PD-L1 expression $\geq 1\%$ with at least 75 randomized participants with tumor cell PD-L1 expression 1% - 49%, and at least 75 randomized participants with tumor cell PD-L1 expression $< 1\%$, based on central laboratory results.

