9.1.2 Clinical Outcomes Assessments

The evaluation of PROs is an increasingly important aspect of clinical efficacy and safety in oncology trials. Such data provide an understanding of the impact of treatment from the participant's perspective and offer insights into participant experience that may not be captured through physician reporting.

Participants will be asked to complete the NSCLC-SAQ, the FACT-G7, the 5 Level EQ-5D Questionnaire (EQ-5D-5L), the PGIS and the PGIC at designated study visits. When possible, participants should complete the PRO measures prior to any other study related procedure or assessments during study visits. Assessments will be completed prior to dosing on Day 1 of each cycle from Cycle 1 (with the exception of the PGIC which will be completed at each cycle from Cycle 2; see Section 2 Schedule of Activities). PRO measures will be completed electronically during the study and at Safety and Survival Follow-up.

The PROs should be completed in the following order:

- 1) NSCLC-SAQ
- 2) FACT-G7
- 3) EQ-5D-5L
- 4) PGIS
- 5) PGIC (except for C1D1 when it is not completed)

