10.4.4 Exploratory Endpoint(s)

Table 10.4.4-1: Exploratory Endpoints

Exploratory Endpoint	Description	Timeframe
Pharmacokinetics		
Ctrough and Ceoi	Summary statistics to assess attainment of steady state: geometric means and coefficients of variation, by treatment and by day, Ctrough plots versus time	Time from first study intervention up to last treatment of study drug or discontinuation, or Cycle 17, whichever occur first.
Immunogenicity		

Incidence of ADA to BMS-986207, nivolumab, and ipilimumab
 
Baseline ADA-positive participant is defined as a participant who has an ADA-detected sample at baseline
 
ADA-positive participant is a participant with at least 1 ADA-positive sample relative to baseline after initiation of the treatment
 
Summary measures of ADA titers and kinetics (onset and duration)
 
Assessments of ADA effect on efficacy, safety, and PK
	
Frequency distribution of baseline ADA-positive participants and ADA-positive participants after initiation of the treatment for each of BMS-986207, nivolumab, and ipilimumab.
 
Summary statistics/plots of ADA titers.
 
Table of ADA onset and duration.
 
Summary table/plot of ORR and occurrence of select AEs by ADA status.
 
Plots of PK parameters/exposures by ADA status may be generated as part of a population PK analysis and reported separately.
	Time from first study intervention up to last treatment of study drug or discontinuation, or Cycle 17, whichever occur first.
Biomarker Analysis		
Summary measures of change (or % change) from baseline in various biomarkers in the tumor and peripheral blood	Summary statistics/plots by planned study day and dose in each arm. Plots of the time course of biomarkers by treatment arm	Time from first study intervention up to last treatment of study drug or discontinuation, or Cycle 17, whichever occur first.
Clinical Outcomes Assessments Analysis		
NSCLC-SAQ total score based on the PGIS and PGIC as anchor measures	Summary statistics of change in NSCLC-SAQ total score based on the PGIS and PGIC as anchor measures tabulated by treatment arm and time points	Time from randomization until death, loss to follow-up, withdrawal of consent, or conclusion of the study, whichever comes first, for a period of up to 4 years from randomization.

Table 10.4.4-1: Exploratory Endpoints

Exploratory Endpoint	Description	Timeframe

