NSCLC-SAQ total score and FACT-G7	Mean change from baseline in NSCLC-SAQ total score and FACT-G7 by treatment arm	Time from randomization until death, loss to follow-up, withdrawal of consent, or conclusion of the study, whichever comes first, for a period of up to 4 years from randomization.
EQ-5D-5L utility index and EQ VAS scores	Mean change from baseline in EQ-5D-5L utility index and EQ VAS scores by treatment arm	Time from randomization until death, loss to follow-up, withdrawal of consent, or conclusion of the study, whichever comes first, for a period of up to 4 years from randomization.

Abbreviations: ADA, anti-drug antibody; AE, adverse event; Ceoi, end of infusion concentration; Ctrough, observed serum trough concentration; EQ VAS, EuroQol visual analog scale; FACT-G7, Functional Assessment of Cancer Therapy - General - 7 item version; NSCLC-SAQ, Non Small Cell Lung Cancer Symptom Assessment Questionnaire; ORR, objective response rate; PGIC, Patient Global Impression of Change; PGIS, Patient Global Impression of Severity; PK, pharmacokinetic.

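### The exploratory patient-reported scores are summarised only as raw mean change from baseline by arm, with no baseline-adjusted or repeated-measures estimate

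*Combined protocol and SAP*

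**What the plan says.** The exploratory objective is "To characterize changes in disease related symptoms and health-related quality of life in participants with Stage IV NSCLC". Table 10.4.4-1 (Section 10.4.4) serves it with "Mean change from baseline in NSCLC-SAQ total score and FACT-G7 by treatment arm", and the health-status objective with "Mean change from baseline in EQ-5D-5L utility index and EQ VAS scores by treatment arm". Neither row names a visit, model, covariate, interval or rule for missing scores. The stated timeframe runs from randomisation for up to 4 years. The neighbouring row, which uses the NSCLC-SAQ with its two anchor measures, goes slightly further: its summaries are "tabulated by treatment arm and time points".

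The data would support more. Section 9.1.2 states: "Assessments will be completed prior to dosing on Day 1 of each cycle from Cycle 1". Table 2-2 repeats this per-cycle schedule for the treatment period. After treatment, Table 2-3 collects NSCLC-SAQ, FACT-G7 and EQ-5D-5L at the three safety follow-up visits and then in survival follow-up, every 12 weeks from the third of those visits.

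Section 10.4 presents itself as a summary for the primary and secondary endpoints and leaves missing-data procedures to a SAP still to be finalised. Section 10.4.5 sends the PK and biomarker exploratory analyses to the SAP and the NSCLC-SAQ change threshold to a separate plan. Section 5.4.9 describes the separate PRO plan in terms of psychometric work. None of these names a method for the by-arm change scores.

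**The concern.** A table of mean changes by randomised arm invites the reader to subtract one mean from the other. Section 5.4.9 encourages this by offering the NSCLC-SAQ as context for the efficacy and safety results. That subtraction has three weaknesses.

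- Subtracting the baseline score is not the same as adjusting for it. Unless baseline and follow-up are perfectly correlated, the change score adds noise that a baseline covariate would remove.
- A chance baseline difference between arms passes into the difference in change, in the opposite direction.
- With repeated visits and no model, a plain mean at a later visit uses only those who supplied a score. If the reasons for missing scores differ by arm, the two means describe differently selected people.

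At stake is how well a small, 2:1 randomised dataset describes symptoms and quality of life. No decision rule depends on it.

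**Working it through.** The documents give no SD, effect size, alpha or sample size for any patient-reported score, so there is no stated figure to reproduce.

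**Inputs.** About 180 randomised 2:1 (Section 5.2), hence 120 and 60. The correlation rho between baseline and follow-up is an assumption, shown at 0.3, 0.5 and 0.7. Scores are in SD units, with equal variance at baseline and follow-up, one visit and complete data.

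**Precision.** Let f = sqrt(1/120 + 1/60) = sqrt(0.025) = 0.158.

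- Raw change: SE = f × sqrt(2(1 − rho))
- Baseline-adjusted: SE = f × sqrt(1 − rho²)
- Variance ratio: (1 − rho²) / (2(1 − rho)) = (1 + rho)/2

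| rho | SE raw change | SE adjusted | Variance ratio | 95% half-width, raw vs adjusted (1.96 × SE) |
|---|---|---|---|---|
| 0.3 | 0.187 | 0.151 | 0.65 | 0.37 vs 0.30 |
| 0.5 | 0.158 | 0.137 | 0.75 | 0.31 vs 0.27 |
| 0.7 | 0.122 | 0.113 | 0.85 | 0.24 vs 0.22 |

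The SE falls by 1 − sqrt(0.65) = 19% at rho 0.3 and by 1 − sqrt(0.85) = 8% at rho 0.7. In participants, 1/0.65 = 1.54 and 1/0.85 = 1.18, so adjustment is worth 18% to 54% more people.

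**Baseline imbalance.** The baseline difference between arms has SE 0.158 SD, so a difference of 1.96 × 0.158 = 0.31 SD lies at the edge of the 95% chance range. With no treatment effect, it shifts the raw change difference by −(1 − rho) × 0.31. At rho 0.5 that is about 0.155 SD, as large as the SE of the raw change difference itself.

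**Selection (illustration only).** Section 10.2 assumes a control median PFS of 5 months and HR 0.605, for PD-L1 ≥ 1%. Apply these to all 180 as exponential times, with control hazard ln 2/5 = 0.139 per month and 4.345 weeks per month.

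- Week 24: 0.629 × 120 ≈ 76 in Arm A and 0.465 × 60 ≈ 28 in Arm B are progression-free.
- Week 48: 0.396 × 120 ≈ 48 and 0.216 × 60 ≈ 13.

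These are not questionnaire dropout rates, because collection continues after treatment stops. They show only that the participants still on the cycle schedule could differ between arms in number and prognosis.

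**Size of a feasible model.** Eighteen cycles give 17 post-baseline Day 1 visits. An unstructured covariance over all of them has 17 × 18/2 = 153 parameters per score, with about 60 control participants before any attrition. Four visits would need 4 × 5/2 = 10.

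**The case against.** The strongest reply is that no comparison is planned. The PFS and OS objectives between the arms are worded as comparisons, whereas the patient-reported objectives are worded as characterisation. Table 10.4.4-1 states no difference, test or hypothesis for these scores. That is correct. A reader might infer that the protocol has chosen an inferior method for a formal arm comparison, and the documents do not support that. The precision figures apply only to a difference the reader forms from the table.

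Two further inferences also go too far. The first is that baseline and repeated visits are ignored. Baseline is used by subtraction, and the two rows are silent about visits while the adjacent row tabulates by time point. The second is that means are taken among those still reporting and that progression ends collection. No observed-case rule is written, and three of the instruments continue in follow-up. Missing-data handling is also deferred to a SAP not among the documents, which may yet supply a model.

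The reply is also right that the numerical gain rests on an assumed rho and a single complete visit, so it does not measure the benefit of a longitudinal model. A model over every cycle would be unworkable, and 17 visits × 4 scores = 68 intervals would turn a description into unplanned inference.

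What remains is that the plan reports these scores by randomised arm and names no baseline-adjusted or longitudinal estimate, although it collects the data for one.

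**Conclusion.** The point stands as a low-cost improvement to exploratory endpoints. The plan states only raw mean change by arm for these rows. A by-arm difference taken from it has 1.18 to 1.54 times the variance of a baseline-adjusted one for rho between 0.7 and 0.3, and is exposed to chance baseline imbalance and to selective missingness. The variance figures assume equal variances, one visit, complete data and a correlation the documents do not give. The missingness concern is qualitative, because there is no figure for questionnaire completion. The primary PFS analysis and the go criteria do not use these scores.

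**What to change.** Keep the raw means by arm as a descriptive table, and state the visits. In Table 10.4.4-1 and the SAP, add for each of the four scores a mixed model for repeated measures on change from baseline with:

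- baseline score, arm, visit, arm-by-visit, baseline-by-visit, PD-L1 category (three levels) and histology;
- a prespecified set of early on-treatment cycles with adequate numbers in both arms (for example Cycles 2 to 5, giving 4 × 4 = 16 intervals across the scores);
- an unstructured covariance, with a named simpler structure as fallback if it does not converge.

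Report adjusted arm means and their difference with 95% CI at each chosen visit, labelled as exploratory estimates with no hypothesis tests. State that the estimates apply to scores while alive, so that values after death are undefined and not treated as missing. State the missing-at-random assumption for living participants who miss a score, and say whether safety follow-up scores falling near a chosen visit are used.

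The cost is SAP wording and one extra model per score, with no new data. The downside is several exploratory intervals without multiplicity control, which the report should say plainly.

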10.4.5 Other Analyses

Other analyses may include analyses of assessments which are not defined as endpoints, that need to be prespecified and not necessarily be reported in the clinical study report (CSR), such as, but not limited to, exploratory PK and biomarkers .

PK and biomarker exploratory analyses will be described in the SAP finalized before database lock. Population PK and exposure response analyses may also be conducted and would be the subject of a separate report. Additional pharmacodynamic analyses may be done and will be presented separately from the main CSR.

Analyses related to estimation of the meaningful change threshold for the NSCLC-SAQ will be described in a separate PRO psychometric analysis plan.

10.5 Interim Analyses

10.5.1 Safety Continuous Monitoring

A Bayesian continuous monitoring framework will be utilized to monitor for toxicity for a safety-evaluation period of 12 weeks of treatment and detect safety signals that may lead to changes in study conduct.⁴² In addition to the study DMC, a SMT consisting of BMS research and development representatives (including clinical development, drug safety and statistics) and external representatives (including selected investigators) will regularly meet to evaluate the

accumulating unblinded safety data of participants of the study. If the specified safety boundary (number of AEs) is exceeded in Arm A, the DMC will be contacted for additional evaluations of unblinded data as needed.

For this type of monitoring, the proportion of TRAEs of Grade 3 to Grade 4 is used to provide formal monitoring boundaries. These boundaries were established using a prior distribution of Beta(0.66, 1.37), which is a weak informative prior reflecting the approximate proportion of Grade 3 to Grade 4 TRAEs in the nivolumab plus ipilimumab arm in Study CA209227 (ie, 33%). The posterior distribution at any time point is Beta(0.66 + n, 1.37 + [m-n]), where n is the number of participants observed with Grade 3 to Grade 4 TRAEs, and m is the total number of safety-evaluable participants. (For the definition of safety-evaluable participants, see [Section 10.3](#)).

The monitoring function for toxicity is defined as the posterior probability of (Grade 3 to Grade 4 TRAEs > 40% | cumulating data) > 0.85. This criterion implies that there is a greater than 85% predictive probability that the aggregate toxicity rate in Arm A is larger than 40%. It will be applied after at least 8 randomized participants in Arm A are safety-evaluable and can be performed on a continuous basis afterwards. The resulting boundaries are presented in Table 10.5.1-1. This monitoring boundary criterion is not binding.

If, anytime during the study (first 126 participants), this Grade 3 to Grade 4 TRAE proportion reaches the pre-specified threshold for toxicity, then, taking into account all available safety information, additional evaluation will be conducted to allow a complete by treatment arm safety assessment and risk benefit evaluation.

Table 10.5.1-1: Safety Continuous Monitoring Boundary for Arm A

Number of Safety-evaluable Participants in Arm A ^a	Toxicity Boundary (# Evaluable Participants with Event) for > 85 Probability of TRAE > 40%
8	5
9-10	6
11-12	7
13-14	8
15-16	9
17-19	10
20-21	11
22-23	12
24-25	13
26-28	14
29-30	15
31-32	16
33-35	17

Table 10.5.1-1: Safety Continuous Monitoring Boundary for Arm A

Number of Safety-evaluable Participants in Arm A ^a	Toxicity Boundary (# Evaluable Participants with Event) for > 85 Probability of TRAE > 40%
36-37	18
38-40	19
41-42	20
43-44	21
45-47	22
48-49	23
50-52	24
53-54	25
55-57	26
58-59	27
60	28

Abbreviation: TRAE, treatment-related adverse event.

^a Additional thresholds for the monitoring of > 60 participants will be calculated by the Statistician.

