Participants, investigators, and site staff will be blinded (single-blind) to treatment assignment. The Data Monitoring Committee (DMC) and Sponsor will be unblinded to treatment assignment for the purpose of safety evaluation. Treatment information access will not be used by the Sponsor to perform by-arm efficacy analyses.

All participants will be treated for up to 2 calendar years from start of study intervention regardless of treatment delays (up to 18 cycles, 42 days/cycle), until progression, unacceptable toxicity, death, or withdrawal of consent, whichever occurs first. Continuous safety evaluation and tumor assessment will guide the decision to treat a participant with additional cycles of study intervention if the participant has confirmed clinical benefit (up to a maximum of 2 years).

Dose Modification

Intra-participant dose escalation/reduction of BMS-986207 (or its placebo), nivolumab, or ipilimumab (except per weight-based dosing) is not permitted. Dose delays are permitted. Separate assessments of study interventions will be used in considering criteria for dose delay, resumption and discontinuation.

Follow-up Period

Safety Follow-up: At the end of treatment (EOT), all participants will enter a safety follow-up period upon completion of study intervention (up to a maximum of 2 years from first dose of study intervention, if applicable) or once the decision is made to discontinue the participant from treatment. All participants will be evaluated for any new adverse events (AEs) (serious and non-serious) for at least 100 days after the last dose of study intervention.

Imaging Follow-up: Participants that have discontinued treatment without having BICR-assessed disease progression will continue to have radiologic tumor assessments after treatment discontinuation for up to 2 years after last dose of study intervention.

Survival Follow-up: Participants will be followed by phone contact or office visit every 12 weeks (± 2 weeks) until death, loss to follow-up, withdrawal of consent, or conclusion of the study, whichever comes first, for a period of up to 4 years from randomization. A follow-up more than 4 years after randomization could be considered in selected cases if an efficacy signal is apparent.

Study Intervention:

Study Intervention for CA020016		
Medication	Potency	IP/Non-IP/AxMP
Nivolumab	100 mg/vial (10 mg/mL)	IP
Ipilimumab	50 mg/vial (5 mg/mL); 200 mg/vial (5 mg/mL)	IP
BMS-986207	160 mg/vial	IP
Placebo	NA	IP

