5.1.2 Treatment Period

Treatment arms are illustrated in [Figure 5.1-1](#).

The randomized treatment period will assess efficacy and safety of BMS-986207 in combination with nivolumab plus ipilimumab (Arm A) versus nivolumab plus ipilimumab (Arm B).

After central laboratory confirmation of PD-L1 expression, approximately 180 participants (see [Section 10.2](#)) will be stratified by PD-L1 expression (< 1%, 1% - 49%, or ≥ 50%) and tumor histology (squamous versus nonsquamous) and randomized in a 2:1 ratio to:

- **Arm A:** Nivolumab 360 mg Q3W + ipilimumab 1 mg/kg Q6W + BMS-986207 600 mg Q3W
- **Arm B:** Nivolumab 360 mg Q3W + ipilimumab 1 mg/kg Q6W + placebo Q3W

Participants, investigators, and site staff will be blinded (single-blind) to treatment assignment. The DMC and Sponsor will be unblinded to treatment assignment for the purpose of safety evaluation. Treatment information access will not be used by the Sponsor to perform by-arm efficacy analyses. See [Section 5.1.4](#) for further information regarding the DMC and [Section 7.3](#) for further information regarding blinding. Additional information regarding blinding will also be provided in the statistical analysis plan (SAP).

All participants will be treated for up to 2 calendar years from start of study intervention regardless of treatment delays (up to 18 cycles, 42 days/cycle), until progression, unacceptable toxicity, death, or withdrawal of consent, whichever occurs first. Continuous safety evaluation and tumor assessment will guide the decision to treat a participant with additional cycles of study intervention if the participant has confirmed clinical benefit (up to a maximum of 2 years).

Dose reductions of study interventions are not permitted. Separate assessments of study interventions will be used in considering criteria for dose delay, resumption, and discontinuation (see [Sections 7.4.1](#), [7.4.2](#), and [8.1.1](#)).

Physical examinations, vital sign measurements, 12-lead ECG, and clinical laboratory evaluations will be performed at selected times throughout the dosing interval (see [Section 2](#)). Participants will be closely monitored for AEs throughout the study. Samples will be collected before and after study drug administration for PK analysis and pharmacodynamic parameter measurements (see [Section 9.5](#) for further details).

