5.4.7 Rationale for Blinding

Participants, investigators, and site staff will be blinded (single-blind) to BMS-986207 treatment assignment. The DMC and Sponsor will be unblinded to BMS-986207 treatment assignment. A single-blind will be implemented in order to:

- Minimize investigator bias (eg, avoid biased estimate of treatment effect)
- Curtail investigator bias in reporting, classification, and management of AEs
- Permit unblinded safety monitoring by Sponsor (see [Section 10.5.1](#) and additional information will be provided in the SAP) that is in addition to the safety monitoring by the DMC. Treatment information access will not be used by the Sponsor to perform by-arm efficacy analyses.

Single-blinding will be maintained for participants who progress even after disease progression, unless needed by the investigator (eg, selection of subsequent therapies). See [Section 7.3](#) for additional information.

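### Section 10.5.1 seats selected investigators on a team that reviews unblinded safety data, without excluding this trial's own investigators, whom Sections 5.1.2, 5.4.7 and 7.3 keep blinded

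*Combined protocol and SAP*

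**What the plan says.** Section 10.5.1 sets up Bayesian monitoring of Grade 3 to 4 treatment-related adverse events (TRAEs) in Arm A. Besides the DMC, it has an SMT made up of sponsor staff from clinical development, drug safety and statistics, together with outside members. The "external representatives (including selected investigators) will regularly meet to evaluate the" "accumulating unblinded safety data of participants of the study". If the Arm A boundary is exceeded, the DMC is contacted.

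The blinding rules stand elsewhere. Section 5.1.2 says: "Participants, investigators, and site staff will be blinded (single-blind) to treatment assignment". It continues: "The DMC and Sponsor will be unblinded to treatment assignment for the purpose of safety evaluation". The Protocol Summary says the same. Section 5.4.7 repeats the allocation ("The DMC and Sponsor will be unblinded to BMS-986207 treatment assignment") and gives as one purpose of the blind: "Curtail investigator bias in reporting, classification, and management of AEs". Section 7.3 again blinds investigators and site staff, and bars site personnel from treatment assignment until primary database lock, except for an unblinded pharmacist or designee appointed by the site.

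**The concern.** In a trial protocol, an investigator mentioned without qualification is most naturally one of that trial's own. Read that way, 10.5.1 gives some CA020016 investigators regular access to unblinded data that 7.3 withholds from them.

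This matters because the investigator decides whether each adverse event is related to study treatment (Appendix 3, causality assessment), and the Arm A boundary counts only related Grade 3 to 4 events. The first row of Table 10.5.1-1 is 5 participants with an event among 8 evaluable, so at that stage one relatedness call separates 4 events from 5. An investigator who knows which participants receive BMS-986207 may attribute events differently. Investigators also assess PFS, ORR and DOR for secondary endpoints (Table 4-1).

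**Working it through.** No arithmetic applies. The plan gives no figure to reproduce on this point, and the inputs for a numerical effect are absent: the number of investigators on the SMT, the share of participants under their care, and the size and direction of any shift in recorded relatedness. The check is a comparison of the sections.

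1. **Who is blinded.** The Protocol Summary and Sections 5.1.2, 5.4.7 and 7.3 agree: participants, investigators and site staff.
2. **Who is named as unblinded.** The same four places name the DMC and the sponsor.
3. **Who reviews unblinded data under 10.5.1.** Sponsor representatives and external representatives, the latter including selected investigators.
4. **Whether a stated exception covers them.** Each route to treatment information was compared with regular review of accumulating data by an investigator:
   - the site's unblinded pharmacist or designee (7.3): a different role;
   - unblinding of one participant for pregnancy, emergency or unexpected death, or on a non-emergency request discussed with the sponsor (7.3), or after progression if the investigator needs it (5.4.7): case by case, not cumulative;
   - the Unblinded Site Monitor (7.6), the bioanalytical laboratory (9.5) and the independent external statistician (10.5.1.1 and 10.5.1.2): none is an investigator.

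   None of these covers the case.
5. **Whether 5.1.4 settles it.** It names study site investigators separately from the SMT, and its SMT list has no investigator or external member. The list is only a minimum, so it neither forbids nor explains the membership in 10.5.1. It also has the SMT review all available safety data, which sets no limit to totals.
6. **Whether 5.4.7 settles it.** It refers to 10.5.1 for unblinded safety monitoring, but describes that monitoring as the sponsor's. It does not say that investigators join it.
7. **What the boundary needs.** Two Arm A counts: evaluable participants and participants with an event. By-arm information is needed; a list of individual assignments is not. Section 10.5.1 does not say which the SMT sees.

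Steps 1 to 6 show a stated rule in 10.5.1 at odds with the stated blind, with no exception joining them. Step 7 shows that a breach for an individual participant depends on the form of the data.

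**The case against.** The strongest reply is that a reader might infer that 10.5.1 and 7.3 can never both be followed, and the documents do not support that. The blinding sections restrict knowledge of treatment assignment; 10.5.1 grants access to unblinded safety data. An investigator could see two Arm A totals without learning any participant's arm. A strict conflict needs two facts that the plan does not state: that the selected investigators treat CA020016 participants, and that what they see reveals arms. This stands, and the conclusion is conditional for that reason. It does not remove the problem, because 10.5.1 excludes neither fact. Section 10.5.1.2 mentions SMT assessment of aggregate data, but only as an example of what might prompt an ad hoc DMC meeting, not as a limit on SMT access.

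A reader might also infer that external members from outside the trial would breach 7.3. They would not. Section 10.5.1 itself grants their access, the blinding sections do not say that their list is exhaustive, and other recipients, such as the bioanalytical laboratory, are likewise not listed in 7.3. For such members the gap is editorial.

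Sections 5.1.2, 5.4.7 and 7.3 leave further blinding detail to the SAP. It might limit SMT access, but the protocol's own sections would still need to be aligned.

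Finally, the consequence is limited. BICR is blinded to arm (9.1.1.3), the boundary is non-binding, and the DMC has its own unblinded reports. This stands too.

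**Conclusion.** The point holds in conditional form. As written, 10.5.1 lets CA020016 investigators review unblinded safety data, and no exception in the blinding sections allows for it. If those investigators treat trial participants and see participant-level or otherwise arm-revealing data, 10.5.1 conflicts with 7.3 and works against a purpose of the blind given in 5.4.7.

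The effect is probably small and cannot be quantified from the documents. It would be confined to the participants of the investigators concerned, who may be few or none, and would fall mainly on relatedness calls. A reader might infer that the primary result is at risk; the documents do not support that, because primary PFS is assessed by BICR and each investigator-assessed efficacy endpoint (PFS, ORR, DOR) also has a BICR version. The wording should still be corrected, because the change is cheap and knowledge of the arm cannot be undone once given.

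**What to change.** In Section 10.5.1, state that investigators and site staff participating in CA020016 do not take part in SMT review of unblinded or by-arm data and may see only pooled, arm-masked summaries. Align the description of SMT membership and access in Section 5.1.4. If external members from outside the trial keep unblinded access, list them in Section 7.3 or the SAP as an editorial alignment.

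A narrower sentence, saying only that no investigator receives participant-level assignments, would remove the literal conflict with 7.3. It would leave by-arm summaries open, and with few evaluable participants an investigator might recognise a patient's distinctive event in them.

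The cost is a few sentences and one working constraint: by-arm SMT review, including the Arm A boundary, is held without trial investigators, whose input is then based on pooled data. No endpoint, sample size or boundary changes.
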